## 14.5. Follow-Up of Adverse Events and Serious Adverse Events

All AEs and SAEs that are deemed possibly related or probably related to PTG-300 must be followed until resolution, until the condition stabilizes, until the event is otherwise explained, or until the subject dies or is lost to follow-up. The Investigator is responsible to ensure that follow-up includes any supplemental investigations as may be indicated to elucidate as completely as practical the nature and/or causality of the AE/SAE. This may include additional laboratory tests or investigations, histopathological examinations, or consultation with other health care professionals.

If a subject dies during participation in the study or during a recognized follow-up period, the Sponsor should be provided with a copy of any post-mortem findings, including histopathology.

#### 15. STATISTICS

Summary statistics for all efficacy, safety, and PK/PD data, along with the estimation of PTG-300's treatment effect, will be provided. A detailed statistical analysis plan (SAP) will be prepared prior to performing any analysis. In case of differences between the protocol and the SAP, the SAP will take precedence.

## 15.1. Study Design and Sample Size Estimation

This is a multicenter, single-arm, open-label study.

This trial is exploratory and no rigid criteria for sample size are pre-specified. The choices are based on risk/benefit assessment of accumulating results. However, there will be at least 80% power for a sample size of 20 subjects to detect a 50% reduction in the number of phlebotomies from baseline. The power calculation is based on a hypothesized effect size of 0.5 (mean change = 1, with SD = 2) over 24 weeks using a 1-sided one-sample t-test at alpha=10% level. Twenty-eight (28) subjects will be enrolled in the study, assuming an approximate 25% dropout.

## 15.2. Demographics/Baseline Comparability

The demographics and baseline characteristics will be summarized by groups, with and without the iron absorption substudy, respectively, and overall using descriptive statistics. Demographics information includes age, sex, race, and ethnicity. Baseline disease characteristics will be included if necessary.

#### 15.3. Data Presentation

Serum chemistries and measurements related to iron studies will be obtained at the clinical site and/or at a central laboratory. The central laboratory value will be used for data presentation and study endpoints. The clinical laboratory value may be used for clinical decision making.

#### **15.4.** Definition of Baseline

For the phlebotomy frequency, the subjects' pre-study phlebotomy history will serve as the baseline. For serum ferritin and TSAT, measurements obtained during the screening period will serve as the baseline.

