## 5. INTRODUCTION

# 5.1. Background

Protagonist Therapeutics, Inc. (Protagonist) is developing PTG-300, an injectable peptide mimetic of the endogenous hormone hepcidin, as a potential treatment for hereditary hemochromatosis (HH).

HH is a rare genetic disorder that disrupts the body's regulation of iron, causing the body to absorb too much iron from the diet. In HH types I-III, mutations in genes encoding hepcidin regulators, or hepcidin itself lead to diminished production of hepcidin, thus decreasing the inhibitory effect of hepcidin on duodenal iron absorption and causing clinical iron overload (Brissot 2011). Hepcidin deficiency leads to increased circulating transferrin saturation, and ultimately, iron accumulation in organs such as the liver, pancreas, heart, and bone. Iron in excess may induce or favor the development of complications such as cirrhosis, liver cancer, diabetes, heart failure, hypogonadism, but also, complaints such as asthenia and disabling arthritis. If left untreated, HH can lead to morbidity and eventually death (Katsarou 2019). Therapeutic phlebotomy to reduce iron loading is standard treatment for HH. The phlebotomy frequency required for a patient is based on serial measurements of their serum ferritin levels and transferrin saturation (Crownover 2013). Therapeutic phlebotomy is highly efficient in removing excess iron and preventing most of the complications associated with excess iron in the body. However, this treatment does not target the biological mechanisms involved in the iron metabolism disturbance.

In a hepcidin-deficient mouse model of hemochromatosis, a minihepcidin was effective for decreasing iron loading in the liver and heart compared to solvent control in mice that were not iron overloaded (Ramos 2012). These observations suggest that a hepcidin mimetic such as PTG-300 may be effective for preventing iron overload in patients with hemochromatosis.

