# **7.1.1.** Screening (Study Day -21 to -1)

After giving written informed consent, subjects will be screened for eligibility according to inclusion/exclusion criteria (see Section 8) within 21 days of dosing. Subjects will continue their individual iron restricted diet throughout the study. During this period liver iron concentration (LIC) will be assessed by magnetic resonance imaging (MRI). Subjects will begin treatment with PTG-300 within approximately 7 days following a regular phlebotomy, with iron parameters measured before (Screening labs) and after the phlebotomy (pre-dose Study Day 1). Each individual subject's pre-phlebotomy serum ferritin level and TSAT will be used as a criterion for phlebotomy during the study, i.e., the threshold at which a phlebotomy should be considered during the study. The serum ferritin level and TSAT obtained during Screening will be used as baseline to assess the change from these measurements post-dosing with PTG-300. All concomitant medications received by the subject beginning 30 days prior to Screening should be collected.

After eligibility has been confirmed, subjects will be enrolled in the study. Those subjects who choose to participate and complete informed consent for the iron absorption substudy will complete their Iron Absorption A session during Screening (See Section 7.1.3 below).

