Subjects will continue treatment by self-administering PTG-300 at home (or in the clinical center as appropriate) for up to 24 weeks based on acceptable safety and tolerability of the drug (Section 7.2). Subjects will return for clinic visits to have safety assessments; serum iron parameters plus soluble transferrin receptor (sTfR), hepcidin and antidrug antibodies (ADA); and efficacy evaluated according to the schedule of assessments.

Subjects' iron parameters will be monitored throughout the study.

Change in Starting Dose: The starting dose may be increased from 10 mg to 20 mg, 40 mg, or 80 mg as appropriate if <2 of the first 4 subjects (or ≤25% of a larger number of subjects) treated at a given dose have both peak and trough TSAT values approximately <40% and no safety signals have been noted.

Criteria for a Phlebotomy: Subjects should undergo an on-study phlebotomy when the subject's serum ferritin levels and TSAT value are higher than the pre-phlebotomy serum ferritin and TSAT values obtained during Screening. In addition, a phlebotomy may be performed when the Investigator assesses it is necessary for subject care.

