# NOTE: Subjects may require additional visits one day post dose to assess PD effect for dose escalation.

- a Subjects may be rescreened if necessary. Rescreening is considered conducting screening tests outside of the 21-day screening window.
- b Clinical visits should be conducted within an approximately 2-day window (±2 days). All study procedures should occur before study drug administration except as indicated (i.e., PK/PD).

- c Follow-Up procedures are to occur approximately 4 weeks after last dose whether the subject completes the study or terminates early.
- d Subjects enrolled at sites in the United States (US) must sign HIPAA authorization prior to the conduct of any study-specific procedures.
- e Must be conducted within approximately 7 days of PTG-300 dosing. Screening serum iron parameters must be collected before phlebotomy. Note: the prephlebotomy serum ferritin level and TSAT will be used as the subject's individual phlebotomy threshold for the study, i.e., the designated level at which a phlebotomy will be considered.
- f If a subject meets pre-specified criteria for phlebotomy during a visit, schedule a phlebotomy as soon thereafter as possible.
- g Additional tests or examinations, including physical exams, may be conducted as necessary.
- h For women of childbearing potential only.
- i Iron Absorption A is conducted prior to starting PTG-300 (i.e., after the phlebotomy performed during the Screening period). Iron Absorption B should be conducted after approximately 4 to 6 weeks of PTG-300 treatment (one day after PTG-300 administration between Week 4 and Week 6). See Table 3 for the Iron Absorption substudy schedule of events.
- j Study drug administration: PTG-300 is administered weekly or twice weekly. See Section 7.1.2 for details for monitoring TSAT and dose escalation.
- k See Appendix 1 for list of clinical laboratory tests. At Visits 3, 5, and 7, tests will include chemistry and CBC panel only (no urinalysis).
-  These tests should be conducted every 4 weeks at each clinic visit as well as each time point that PTG-300 PK blood samples are collected. In addition, iron parameters must also be measured whenever a subject's dose is escalated (See Section 13.1 and Appendix 2). Additional tests may be obtained as outlined in *Individual Subject Dose and Schedule Escalation* in Section 7.1.2.

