## 10. TREATMENT OF SUBJECTS

# 10.1. Description of Study Drug

This study is a single-arm, open-label study; there is no placebo or comparator used.

PTG-300 will be provided by Protagonist.

PTG-300 is formulated in an aqueous buffered solution and prefilled at 0.5 mL and 1.0 mL into a 1-mL glass syringe. Study drug will be administered by subcutaneous (SC) injections, using a needle and a pre-filled syringe.

Fe will be provided by Protagonist as a ferrous sulfate solution for oral administration.

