## 12. ASSESSMENT OF EFFICACY

## 12.1. Clinical Endpoints

#### 12.1.1. Phlebotomy and Iron Parameters

Intermittent therapeutic phlebotomy is standard of care for patients with HH. During the study the timing of a subject's phlebotomy will be based on their established TSAT and serum ferritin pre-phlebotomy threshold.

During the screening phase, subjects will have a phlebotomy within approximately 7 days prior to PTG-300 dosing. Each individual subject's pre-phlebotomy serum ferritin level will be used as their individual phlebotomy threshold, i.e., the designated level at which a phlebotomy may be performed in the study.

Subjects' iron parameters will be monitored throughout the study. A subject will receive a therapeutic phlebotomy during the study if his/her TSAT and serum ferritin is above their prephlebotomy level at Screening.

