## 15.5. Analysis of Efficacy Data

Efficacy data will be analyzed for all the subjects included in the Intent-to-Treat Analysis Set defined below.

In general, continuous endpoints will be summarized by standard descriptive statistics (mean, standard deviation, median, minimum, and maximum). Categorical endpoints will be summarized by frequencies and percentages.

Hypothesis testing will be performed by the t-test for each of the change from baseline endpoints listed below to evaluate if the change is significantly different from zero. P-value will not be adjusted for multiple comparisons since this is an early phase safety and proof of concept study. In addition, the point estimate (i.e., mean and/or median) and the confidence interval associated

with the estimate will be provided. Kaplan-Meier estimate will be applied for the time to first phlebotomy data.

Data collected for subjects electing to participate in the iron absorption substudy will be analyzed separately in addition to the analyses for all the Intent-to-Treat subjects. Serum iron, Fe, TSAT, serum ferritin, sTfR, and transferrin pertaining to the iron absorption substudy will be analyzed for the subgroup as defined as Iron Absorption analysis set below.

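### The ferritin and TSAT baseline is drawn before the screening phlebotomy, so at early visits the tested change combines phlebotomy and PTG-300

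*Combined protocol and SAP*

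**What the plan says.** Section 15.4 states: "For serum ferritin and TSAT, measurements obtained during the screening period will serve as the baseline". Section 7.6 has the same definition. Neither says which side of the phlebotomy the sample falls on, but two other places do. Table 2 footnote e says: "Screening serum iron parameters must be collected before phlebotomy". Section 7.1.1 identifies the Screening labs as the pre-phlebotomy sample and the pre-dose Day 1 sample as the post-phlebotomy one, and it takes the Screening value as the starting point for change after dosing.

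The phlebotomy is part of the design. Section 12.1.1 says: "During the screening phase, subjects will have a phlebotomy within approximately 7 days prior to PTG-300 dosing".

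Section 7.6.1 lists change in ferritin, change in TSAT, and the time each spends below baseline as efficacy endpoints. Section 15.5 applies a t-test to the change endpoints "to evaluate if the change is significantly different from zero". It names no visit, alpha or sidedness for these tests. It refers to a list of endpoints that does not follow, so that ferritin and TSAT are among those tested is read from 7.6.1. Section 10.1 confirms that "there is no placebo or comparator used".

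**The concern.** An iron-lowering procedure sits between the baseline and every post-dose value. Section 5.1 says of it: "Therapeutic phlebotomy is highly efficient in removing excess iron". Shortly after it, zero is not the change to expect in a subject who gets no benefit from the drug. With a single arm, the reference value is the only control. A significant early fall from Screening would show that phlebotomy plus PTG-300 lowers ferritin or TSAT, not that PTG-300 does.

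The duration endpoints share the problem. A subject can enter treatment already below baseline because of the phlebotomy, and those weeks would count as time below baseline whatever the drug does.

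The value that would separate the two effects is collected before the first dose on Day 1. No analysis of the full study population uses it as a reference.

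**Working it through.** **The plan's own figure.** Section 15.1 claims at least 80% power for n = 20, effect size 0.5 (mean change 1, SD 2), one-sided alpha 10%. The noncentrality is 0.5 × √20 = 2.236 and the critical value on 19 df is 1.328, which gives 81.7%. The claim reproduces, but it concerns the phlebotomy count. No corresponding figure exists for ferritin or TSAT.

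**Inputs from the protocol.** The phlebotomy is up to about 7 days before Day 1 (7.1.1); 7 days is used. Eligible phlebotomy rates run from 0.25 per month to just under 1 per month (8.1), so intervals L run from just over 1 month to 4 months: 30.4, 60.9, 91.3 and 121.8 days for 1, 2, 3 and 4 months. Visits are at Days 15, 29, 57, 85, 113, 141 and 169 (Table 2). n = 20 is taken from 15.1.

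**Assumptions, because the protocol gives no figure.** No drug effect. Fall after phlebotomy of 0.2, 0.5 or 1.0 SD of the change score. Linear regain to the Screening level over L. Two-sided 5% test.

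**Formulas.** Share of the fall remaining at Day D: f = max(0, 1 − (D − 1 + 7)/L). Standardised mean change: δ = fall × f. False rejection: P(|T| > 2.093), with T noncentral t on 19 df and noncentrality δ√20.

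Example, 3-month interval, Day 15, 0.5 SD fall: f = 1 − 21/91.3 = 0.770; δ = 0.385; noncentrality 1.72; rejection 37%.

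**False rejection by visit, 0.5 SD fall, change from Screening:**

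| Interval | Day 15 | Day 29 | Day 57 | Day 85 | Day 113 |
|---|---|---|---|---|---|
| 1 month | 10% | 5% | 5% | 5% | 5% |
| 2 months | 29% | 15% | 5% | 5% | 5% |
| 3 months | 37% | 26% | 10% | 5% | 5% |
| 4 months | 42% | 33% | 18% | 8% | 5% |

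**Sensitivity at Day 15 to the assumed fall:**

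| Interval | 0.2 SD | 0.5 SD | 1.0 SD |
|---|---|---|---|
| 1 month | 6% | 10% | 26% |
| 2 months | 9% | 29% | 79% |
| 3 months | 10% | 37% | 90% |
| 4 months | 11% | 42% | 94% |

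**Duration endpoints.** On the same model an untreated subject first returns to the Screening level L − 7 days after Day 1, for example 91.3 − 7 = about 84 days at a 3-month interval, whatever the size of the fall. This is only the first stretch below baseline; the total also depends on later phlebotomies.

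**What a Day 1 reference would do.** Untreated values climb from Day 1 by 0.5 × (D − 1)/L. At 3 months that is 0.077, 0.153, 0.307 and 0.460 SD at Days 15, 29, 57 and 85. Assuming the same SD, a two-sided 5% test falsely shows a reduction in 1.1%, 0.4% and 0.1% of trials at Days 15, 29 and 57. It rejects in either direction in 6%, 10%, 26% and 50% at Days 15 to 85, almost always as a rise. Now take a drug that only prevents the regain, leaving values 0.5 SD below Screening at Week 25. The Screening contrast then has 56% power (two-sided 5%), and the Day 1 contrast has only its null rate of 5%.

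**The case against.** The strongest reply is that Screening is a sensible reference. It is the subject's phlebotomy threshold: Section 7.1.2 calls for phlebotomy when "serum ferritin levels and TSAT value are higher than the pre-phlebotomy serum ferritin and TSAT values obtained during Screening". Change from it asks whether subjects stay below the level at which they would be treated, which fits the rationale in 5.1.1 of preventing iron overload. The Day 1 value is not neutral either, since untreated values rise from it. This stands, and it is why Day 1 should be added and not substituted.

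The size is also uncertain. The percentages depend on an assumed fall, applied alike to ferritin and TSAT although 5.1 says nothing about how TSAT recovers. They also depend on the mix of intervals, and at the shortest eligible interval little is left by Day 15. This too stands; only the direction at early visits follows from the text.

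A post-phlebotomy, pre-drug sample is not wholly absent from the analysis. Iron Absorption A provides one and 15.5 analyses the substudy data. But that covers about 6 subjects, and no contrast of iron parameters between A and B is spelled out.

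Finally, the study is exploratory, p-values are unadjusted, and a detailed SAP is still to come. That lowers the stakes, but Section 15 also promises an estimate of the drug's treatment effect, so the reference matters.

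A reader might go further in three ways that the documents do not support:

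- **That the Week 25 test is biased by the screening phlebotomy.** On the model above that effect is gone by then. On-study phlebotomies can affect late values, but that is a different mechanism and not a consequence of the baseline.
- **That the phlebotomy endpoints share this bias.** Under 15.4 the baseline for frequency is the phlebotomy history, not the Screening draw. Starting the clock just after a phlebotomy matches the usual interval between phlebotomies, and any shortfall in the count changes sign with that interval.
- **That early p-values must be removed.** Correct labelling and a second reference are enough.

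**Conclusion.** The concern holds for early visits and for the two duration-below-baseline endpoints. As written, the plan would credit part of the screening phlebotomy's effect to PTG-300 there. That follows from the sequence of draw, phlebotomy and dose, together with a test against zero in a single arm.

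The size cannot be fixed from the documents. The Day 15 range of 6% to 94% covers 1- to 4-month intervals and falls of 0.2 to 1.0 SD. It rests on linear regain, n = 20 and a two-sided 5% test, none of which the plan specifies for these endpoints. With a 0.5 SD fall the excess is gone by Day 29, 57, 85 and 113 for 1-, 2-, 3- and 4-month intervals. The baseline in 15.4 is not wrong in itself; it lacks a supplementary contrast and a plain statement of what the early change measures. This should be fixed before analysis.

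**What to change.** In Sections 7.6 and 15.4, and in the SAP:

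1. Name the pre-phlebotomy Screening draw explicitly as the baseline. The present wording does not single out one sample for substudy subjects, who also have iron parameters drawn after the phlebotomy but still within Screening.
2. Add the post-phlebotomy, pre-dose Day 1 draw as a second reference.
3. Report the Screening-to-Day 1 step, and the change in ferritin and TSAT from both references at each visit, with confidence intervals.
4. State that an early fall from Screening is the combined effect of phlebotomy and drug. Base any early claim of a drug-related reduction on the change from Day 1.
5. Keep the Screening contrast for later visits, where Day 1 is conservative and has little power for a drug that only prevents regain.
6. Label the duration endpoints as time below the pre-phlebotomy threshold, combining phlebotomy and drug.

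The cost is wording and a few extra summaries. Day 1 iron parameters are already in Table 2, and under Section 15 the SAP is still to be prepared and takes precedence over the protocol. The downside is that the early change will look less favourable. The phlebotomy threshold and all clinical management stay as they are.

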## 15.5. Analysis of Efficacy Data

Efficacy data will be analyzed for all the subjects included in the Intent-to-Treat Analysis Set defined below.

In general, continuous endpoints will be summarized by standard descriptive statistics (mean, standard deviation, median, minimum, and maximum). Categorical endpoints will be summarized by frequencies and percentages.

Hypothesis testing will be performed by the t-test for each of the change from baseline endpoints listed below to evaluate if the change is significantly different from zero. P-value will not be adjusted for multiple comparisons since this is an early phase safety and proof of concept study. In addition, the point estimate (i.e., mean and/or median) and the confidence interval associated

with the estimate will be provided. Kaplan-Meier estimate will be applied for the time to first phlebotomy data.

Data collected for subjects electing to participate in the iron absorption substudy will be analyzed separately in addition to the analyses for all the Intent-to-Treat subjects. Serum iron, Fe, TSAT, serum ferritin, sTfR, and transferrin pertaining to the iron absorption substudy will be analyzed for the subgroup as defined as Iron Absorption analysis set below.

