# 7.6. Endpoints

**Baseline Definition:** The serum ferritin level and TSAT obtained during Screening will be used as baseline.

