## **7.6.1.** Efficacy

- Change from baseline in serum ferritin.
- Duration of time that serum ferritin is below baseline measurement.
- Change from baseline in TSAT.
- Duration of time that TSAT is below baseline measurement.
- Time to first phlebotomy after dosing.

- Change in frequency of phlebotomies based on historical phlebotomy data (24 weeks).
- Proportion of subjects who achieve phlebotomy independence.
- Additional Endpoints:
  - SF-36
  - PGI-C
  - Change in iron absorption following the administration of PTG-300. (For subjects completing iron absorption substudy.)
  - PTG-300 pharmacokinetics: PTG-300 concentration as a function of dose and time since last dose.
  - PD: Change from baseline in serum iron, transferrin and sTfR.
  - Change from baseline in LIC assessed by MRI.
  - Incidence of ADA.

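### The on-study phlebotomy trigger equals the ferritin/TSAT baseline, and no rule separates post-phlebotomy values, so rescue pulls these endpoints towards baseline whether or not the drug works

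*Combined protocol and SAP*

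**What the plan says.** **Baseline.** Section 7.6: "The serum ferritin level and TSAT obtained during Screening will be used as baseline". Section 15.4 agrees: "For serum ferritin and TSAT, measurements obtained during the screening period will serve as the baseline". A footnote to Table 2 requires the Screening iron sample to be drawn before the screening phlebotomy, so baseline is a pre-phlebotomy value.

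**Trigger.** Section 7.1.2 calls for an on-study phlebotomy "when the subject's serum ferritin levels and TSAT value are higher than the pre-phlebotomy serum ferritin and TSAT values obtained during Screening". It adds that "a phlebotomy may be performed when the Investigator assesses it is necessary for subject care". Section 12.1.1 first words the threshold on ferritin alone ("Each individual subject's pre-phlebotomy serum ferritin level will be used as their individual phlebotomy threshold") and then on both markers. Table 2 schedules the phlebotomy evaluation at Weeks 5, 9, 13, 17, 21 and 25.

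**Endpoints and analysis.** Section 7.6.1 lists change from baseline in ferritin and in TSAT, and for each a duration endpoint such as "Duration of time that serum ferritin is below baseline measurement". Section 15.5 analyses the ITT set with a "t-test for each of the change from baseline endpoints listed below to evaluate if the change is significantly different from zero", although no list follows in that section. Section 15.6.2 excludes nobody because of a phlebotomy. Section 15.7 deals only with missing data. Section 15 says that a detailed SAP will be written and will override the protocol. The documents reviewed contain no rule for values after an on-study phlebotomy.

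**The concern.** One measurement does two jobs. It is the zero point for change, and it is the ceiling above which iron is removed. A subject in whom the drug fails rises past baseline, is phlebotomised, and returns below it. Those lower values are observed rather than missing, and the subject is still on treatment, so nothing in Sections 15.5 to 15.7 sets them aside.

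The change endpoints are therefore held near zero, and the time-below-baseline clock restarts after each rescue. The subjects with the least drug effect receive the most help. Without a control arm, the four ferritin and TSAT endpoints, which serve Objective 2, cannot separate drug effect from phlebotomy.

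**Working it through.** **1. The plan's own figure.** The only stated power is for phlebotomy count (Section 15.1): effect size 1/2 = 0.5, n = 20, one-sided alpha 10%. The noncentrality is 0.5 × √20 = 2.236 on 19 df, giving power of 81.7%. The stated 80% or more is reproduced. No power is given for ferritin or TSAT.

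**2. Planning rate.** A 50% reduction equal to a mean change of 1 implies 2 phlebotomies per 24 weeks, or one per 12 weeks (84 days). Section 8.1 admits 0.25 to just under 1 per month. With 168/30.4 = 5.53 months, that is 1.4 to 5.5 per 24 weeks.

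**3. Hand check with an inactive drug.** Measure ferritin relative to baseline in units of the fall from one phlebotomy. Assume linear re-accumulation over T days and TSAT tracking ferritin:

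level = -1 + (days since screening phlebotomy)/T - (number of on-study phlebotomies)

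Take T = 84 and Day 1 at 3.5 days after phlebotomy (mid-range of the 7 allowed).

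- No rescue, Day 169: -1 + 171.5/84 = +1.04. Baseline is crossed after 84 - 3.5 = 80.5 days, so time below is 80.5/168 = 48%.
- With rescue: at Day 85 the level is -1 + 87.5/84 = +0.04, which triggers a phlebotomy. Week 25 becomes 1.04 - 1 = +0.04.

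**4. Noise-free simulation.** Same model, phlebotomy 1–7 days after a triggering visit, T varying between subjects. Week 25 change is in the same units.

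| Historical rate | Week 25, rescue / none | Time below, rescue / none |
|---|---|---|
| About one per 12 weeks (±30%) | -0.15 / +1.1 | 84% / 47–48% |
| Slowest eligible (0.25 per month) | -0.59 / +0.41 | 85% / 70% |
| Spread over 0.25–1 per month | about +0.1 / +2.5 | 69% / 31–32% |

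**5. Independent simulation with measurement error.** n = 20 per trial, fall per phlebotomy 15–50% of baseline, measurement CV 5–20%, two-sided 5% t-test. These four settings other than n are assumptions; the documents give no values. At one phlebotomy per 12 weeks:

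| | Rescue values kept | No rescue |
|---|---|---|
| Week 25 mean change | -5% to +7% | +17% to +58% |
| Trials with a significant Week 25 rise | 0.2–12% | 61–100% |
| Mean over visits | -3% to -13% | +2% to +6% |
| Trials with visit mean significantly below zero | 12–100% | under 1% |
| Time below baseline | 63–80% | 48–49% |

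With rates spread over the eligible range (CV 10%), Week 25 is +10% to +13% with rescue, against +38% to +128% without. Near one per 5 weeks (30% fall) it is +22% against +115%.

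**6. What rescue does not explain.** At Weeks 3 and 5 (planning rate, 30% fall) the mean is about -23% and -18% with or without rescue. That dip comes from starting drug shortly after the screening phlebotomy and comparing with a pre-phlebotomy baseline.

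**7. Testing remedies in the noise-free model.** Ending the duration clock at the first on-study phlebotomy gives 48%, which equals the no-rescue figure. Carrying forward the last pre-phlebotomy value gives +0.18 at Week 25, so it recovers (0.18 + 0.15)/(1.11 + 0.15) = 26% of the gap. Over the eligible range it gives +0.33, or (0.33 - 0.06)/(2.52 - 0.06) = 11%.

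**The case against.** **The plan is silent, not wrong.** It never says that post-phlebotomy values are kept, and a later SAP takes precedence. This is fair: inclusion is the default reading, not an explicit rule. But all ITT subjects are analysed and nothing separates these values, so the plan as written leads there.

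**A reader might infer that an inactive drug would appear to hold iron at or below baseline for the full 24 weeks.** The documents do not support that. The trigger in Section 7.1.2 needs both markers above threshold and is formally checked about every four weeks. Fast re-accumulators can therefore sit above baseline at Week 25, and the planned t-test could show a rise. If TSAT did not respond to phlebotomy, ferritin would overshoot further (+9% at 12-week intervals, +58% at 5-week intervals).

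**A reader might also attribute all the time below baseline to rescue.** About 48 of the 84 percentage points at the planning rate arise without any rescue. They belong to the separate screening-phlebotomy issue.

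**A reader might extend the claim to liver iron concentration.** LIC is not a trigger and was not modelled. An effect on it has not been shown.

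**The trial is exploratory, and its power statement concerns phlebotomy.** This is true, and time to first phlebotomy, frequency and independence would reveal rescue use. They do not repair the ferritin and TSAT results. Nor is the count a clean safeguard: in the step 5 simulation an inactive drug gave about 1.05 on-study phlebotomies against 2 historical.

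**Conclusion.** The concern holds in this form. Trigger and baseline are the same measurement, no rule separates values after an on-study phlebotomy, and by default rescue moves ferritin and TSAT towards apparent iron control.

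At the planning rate, an inactive drug ends near baseline (-0.15 of one phlebotomy's fall, or -5% to +7% of baseline) instead of showing a clear rise (+1.1, or +17% to +58%). Time below baseline is 63–84% instead of 47–49%. Over the whole eligible range the pull is in the same direction, but Week 25 can remain above baseline.

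The sizes rest on linear re-accumulation, TSAT moving with ferritin, and assumed falls and measurement error. The direction needs only that ferritin rises between phlebotomies and falls after one.

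**What to change.** In the SAP:

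- (a) Define on-study phlebotomy as an intercurrent event for the ferritin and TSAT endpoints, and end time below baseline at the first one.
- (b) Report change from baseline using only values up to the first on-study phlebotomy, beside the all-values analysis labelled as drug plus phlebotomy. Do not base a drug-effect claim on the all-values result alone. Give the number of subjects contributing at each visit. In the step 5 simulations at the planning rate, 65–98% of subjects had at least one on-study phlebotomy, so few and selected subjects would remain late on, and this analysis cannot stand alone at Week 25 either. Carry-forward of the last pre-phlebotomy value may be shown as a sensitivity analysis, noting that it understates the rise and could favour the drug after a discretionary phlebotomy.
- (c) Also report change from the Day 1 pre-dose value. This addresses the early dip, not the rescue effect.
- (d) List the number of on-study phlebotomies beside the LIC results, descriptively only.

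The ferritin-only sentence in Section 12.1.1 and the two-marker wording in Section 7.1.2 should be reconciled, because the event definition depends on them.

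**Cost.** SAP wording and one extra set of tables from data already collected. The ferritin and TSAT results will look less favourable. Sample size, assessments and clinical rules do not change.
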